8.11. Data Monitoring Committee

An independent multidisciplinary DMC will review the progress of the study and perform interim reviews of safety data. A total of 4 scheduled DMC meetings will occur throughout Part 1 and prior to the end of Part 2 of the study as outlined below.

Part 1: Safety Analysis #1

Because GS-5745 has not been administered previously to CF subjects, the DMC will review the unblinded safety data after 10 subjects (~5 active and ~5 placebo) have completed the Week 2 Visit or have prematurely discontinued from the study. Enrollment will continue during the DMC review process.

Part 1: Safety Analyses #2

The DMC will review the unblinded safety data after 30 subjects (~15 active and ~15 placebo) have completed the Week 8 Visit or have prematurely discontinued from the study. Enrollment will continue during the DMC review process.

Part 1: Safety Analyses #3 and Interim Efficacy Analysis

An interim efficacy and safety analysis will be performed when all 60 subjects (~30 active and ~30 placebo) have completed the Week 8 Visit or have prematurely discontinued from the study. The DMC and a select number of Gilead employees not directly involved in the study conduct will review the unblinded data.

With no safety concern, an estimated mean difference in absolute FEV₁% predicted between GS-5745 and placebo being $\geq 5\%$ may trigger the initiation of Part 2. If the mean difference is $< 2\%$, Part 2 may not be initiated. A comprehensive review of safety, FEV₁, FRI and other efficacy data including sputum MMP-9, CFQ-R, SNOT-22, TSQM, and CF exacerbation will be conducted before the decision is made to advance to Part 2 of the study. Enrollment of subjects into Part 2 of the study will be postponed until after the completion of the third DMC and unblinded Gilead review of the data.

Part 2: Safety Analysis #4

The DMC will review the unblinded safety data after 45 subjects (~ 15 in each treatment group) have completed the Week 8 Visit or have prematurely discontinued from the study. Enrollment will continue during the DMC review process.

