3.3.3. Open-Label Extension (OLE)

On the Week 8 visit (-3 to + 4 days) of both Part 1 and Part 2, subjects (active and placebo) will be invited to participate in an OLE treatment period.

- Subjects choosing to participate from Part 1 will receive open-label 600 mg of GS-5745 weekly for 16 additional weeks.
- All subjects choosing to participate from Part 2 will receive open-label 300 mg of GS-5745 weekly for 16 additional weeks.

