4. SUBJECT POPULATION

4.1. Number of Subjects and Subject Selection

Up to 150 subjects who meet the eligibility criteria at screening will be randomized to receive GS-5745 or placebo in Part 1 (60 subjects) and Part 2 (90 subjects). The sub-study for FRI will enroll up to 35 subjects in Part 1 and up to 52 subjects in Part 2 to account for an attrition rate of 15%.

Subjects who fail to meet all the inclusion criteria or who meet any of the exclusion criteria will not be randomized in this study. No waivers for any study entry criteria will be granted.

In order to manage the total study enrollment, Gilead Sciences, Inc. (Gilead), at its sole discretion, may suspend screening and/or enrollment at any site or study-wide at any time.

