6.1.5. Week 8 (-3 to + 4): Primary Endpoint and Open-Label Extension

All Week 8 tests and procedures must be completed prior to participating in the OLE and dosing as indicated in [Table 6-1](#).

Subjects who agree to participate in the OLE portion of the study will be entered into the IXRS to confirm enrollment into the open-label extension after all other procedures as indicated in [Table 6-1](#). The first dose of open-label GS-5745 should be dispensed as directed by IXRS and administered to the subject at Week 8. Sites should train the subject on administration of the study drug at this visit. Subjects will be observed for 30 minutes after the last injection for the first 2 doses.

If the home health option is utilized during OLE, subjects will be dispensed GS-5745 at the visit prior to the scheduled home health visit for Weeks 11, 13 to 15, 17 to 19 and 21 to 23.

Subjects who do not agree to participate in the OLE portion of the study will be discontinued from the study and will be asked to return to the clinic in 30 days for their 30-day Follow-up visit as indicated in [Table 6-1](#).

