## 1. INTRODUCTION

This statistical analysis plan (SAP) describes the statistical analysis methods and data presentations to be used in tables, figures, and listings (TFLs) in the clinical study report (CSR) for Study GS-US-404-1808. This SAP is based on the study protocol Amendment 2 dated 25 May 2016 and the electronic case report forms (eCRF). The SAP will be finalized before database finalization. Any changes made after the finalization of the SAP will be documented in the CSR.

The study was terminated early by the sponsor on 08 June 2017 due to business decision. This SAP describes the analyses to support the synoptic CSR.

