**Figure 1-1. Study Design Schema**

There was a FRI sub-study which required 2 FRI scans (at Baseline and at the Week 8 visit).

Up to 150 subjects with CF  $\geq$  18 years of age were planned to be enrolled.

Subjects randomized to placebo in Part 1 received 4 SC injections per dose. Subjects randomized to placebo in Part 2 would receive 2 SC injections per dose.

The study was terminated after 6 subjects were enrolled in Part 1 of the study. Therefore, Part 2 was not initiated.

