## **2. TYPE OF PLANNED ANALYSIS**

### **2.1. Interim Analyses**

The first DMC safety review was planned when 10 subjects completed the Week 2 visit or discontinued early.

Due to the early study closure, the required number of subjects for the first planned DMC was not reached. Therefore, no DMC interim analyses were performed.

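### The first DMC safety review in Part 1 depends only on a count of 10 subjects, with no latest date, so open-label dosing can begin before it

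*Protocol*

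**What the plan says.** Protocol 8.11 gives the reason for the early review, "Because GS-5745 has not been administered previously to CF subjects", and then its trigger: "the DMC will review the unblinded safety data after 10 subjects (~5 active and ~5 placebo) have completed the Week 2 Visit" or have discontinued. Enrolment is not paused for the review. The section gives no calendar date or longest permitted wait. Section 7.4 describes DMC review as periodic but refers back to 8.11 for the detail.

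On the extension, 3.3.3 states: "On the Week 8 visit (-3 to + 4 days) of both Part 1 and Part 2, subjects (active and placebo) will be invited" to take part. Section 6.1.5 adds: "The first dose of open-label GS-5745 should be dispensed as directed by IXRS and administered to the subject at Week 8". Table 6-1 note n sets two conditions on that dose: the subject elects the extension, and the other Week 8 procedures are finished. Neither involves the DMC.

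Under 4.1 the sponsor "may suspend screening and/or enrollment at any site or study-wide at any time". The SAP reports the outcome. Section 1.2: "The study was terminated after 6 subjects were enrolled in Part 1 of the study". Section 1: "The study was terminated early by the sponsor on 08 June 2017 due to business decision". Section 2.1: "the required number of subjects for the first planned DMC was not reached. Therefore, no DMC interim analyses were performed".

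**The concern.** Review #1 exists to give an independent committee an early look at a drug not previously given to people with CF. Its timing is tied to enrolment speed, while the start of OLE dosing is tied to each subject's own clock. If enrolment is slow, the two can fall in the wrong order: former placebo subjects receive their first active doses, and former active subjects begin up to 16 more weeks of drug, before the committee has seen any data. If enrolment stops short of 10, no scheduled review falls due at all, and routine unblinded safety monitoring rests with the sponsor's internal team.

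**Working it through.** **Inputs.** Week 2 is Day 15, window ±3 days, and Week 8 is Day 57, window −3 to +4 days (Protocol Table 6-1; SAP 4.2.1 repeats Day 57). The rule day = 7 × week + 1 reproduces both: 15 and 57. The trigger is 10 subjects past Week 2 (8.11). The documents give no enrolment rate and no interval from trigger to meeting, so both are assumed below and shown as ranges.

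**Threshold.** Let T10 be the days from the first subject's Day 1 to the tenth subject's Day 1. The first OLE dose falls 56 days after the first subject's Day 1. The trigger is met at T10 + 14 days. OLE dosing comes first when T10 > 56 − 14 = 42 days, or 6 weeks. That is 9 further entries in 6 weeks, or 1.5 per week.

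- OLE dose on Day 54, tenth subject's Week 2 on Day 18: 53 − 17 = 36 days.
- OLE dose on Day 61, tenth subject's Week 2 on Day 12: 60 − 11 = 49 days.
- A lag of L days from trigger to meeting lowers the nominal threshold to 42 − L: 28 days for a 2-week lag, 14 days for a 4-week lag.

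Early discontinuations count towards the 10, so a withdrawal can bring the trigger slightly forward.

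**Illustration.** Assume the 60 Part 1 subjects enter evenly over T weeks, all roll over, none drops out, and visits are on nominal days. Spacing is T/59, T10 = 9T/59, and the count is met at T10 + 2 weeks. A subject is already in the OLE if entry + 8 weeks is earlier than the review.

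| Part 1 entry over | T10 | Count met | In OLE by then | In OLE by meeting, 2-week lag | In OLE by meeting, 4-week lag |
|---|---|---|---|---|---|
| 26 weeks | 4.0 weeks | week 6.0 | 0 | 0 | 5 |
| 52 weeks | 7.9 weeks | week 9.9 | 3 | 5 | 7 |
| 104 weeks | 15.9 weeks | week 17.9 | 6 | 7 | 8 |

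With no lag, the order reverses once T exceeds 6 × 59/9 = 39.3 weeks, about 9 months.

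**Check of a dated limit.** A meeting held by week 7 is 49 days after the first dose. The earliest OLE dose (Day 54) is 53 days after it, so no subject is in the OLE in any row. An 8-week limit (56 days) would not guarantee this.

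A week-7 meeting with a 2- to 4-week lag needs a data cut at week 5 to week 3. Subjects past Week 2 at cut c number floor((c − 2) × 59/T) + 1:

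- T = 26: 3 to 7
- T = 52: 2 to 4
- T = 104: 1 to 2

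About half would be on active drug under 1:1 allocation. At T = 26 with a 2-week lag, the count-based meeting would fall at week 6.0 + 2 = 8.0, so the date would govern there too.

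**The case against.** The strongest case is that Week 8 is not an obvious safety line and that other controls exist.

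- The Part 1 OLE dose equals the blinded dose, 600 mg weekly (3.3.1, 3.3.3). Active subjects simply continue, and placebo subjects meet the same first-dose exposure that active subjects met on Day 1 with no review behind them. Review #1 does not pause enrolment either.
- By the protocol's account, the drug had been given to 221 subjects, at up to 1800 mg IV every 2 weeks (1.3.1), with no drug-related safety signal (1.2.3).
- Unsupervised self-injection in the OLE already waits for DMC and sponsor agreement (5.3, 6.1.6, Table 6-1 note o). Without a DMC review, OLE dosing stays at the clinic or with a home health provider.
- Section 3.5 suspends dosing on defined events, with the DMC sharing the decision to restart. Section 6.1.6 commits the DMC and sponsor to watching injection safety throughout. A sponsor unblinded team follows safety (8.12).
- Up to 75 sites were planned. With all of them open, 1.5 subjects per week is one per site every 75/1.5 = 50 weeks. Staggered start-up would slow this, but quick early enrolment was plausible.
- The power in 4.1 is given for managing total enrolment. It does not describe stopping below 10 while dosing continues.

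These points stand and set the priority low. None of them gives a date for an independent review or makes the first OLE dose wait for one. The DMC charter, which 7.4 mentions, may do so or may provide for ad hoc meetings; it is not among the documents.

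A reader might go further and infer from the SAP that enrolment was slow, or that the six subjects passed into open-label dosing without review. The documents do not support either. The SAP attributes closure to a business decision, gives no entry dates, and does not say how many doses were given or whether anyone entered the OLE. It shows only that the count can go unmet.

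**Conclusion.** The point holds for the protocol text as supplied. Review #1 has a count trigger and no latest date, and the first OLE dose does not depend on it. The order reverses when the first 10 subjects take more than about 6 weeks to enter (36 to 49 days across windows, less any meeting lag). Below 10 subjects the review never falls due. The threshold rests on the visit schedule alone. The numbers already in the OLE rest on assumed even entry, full rollover and no dropout, and should be read as a range.

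It would be too strong to say that OLE subjects had no independent protection, given the self-injection gate and the suspension rules. The trial has closed, so the value lies in the plan as written and in any study that reuses this wording. Confidence is medium because the charter is unseen. This is a cheap improvement of low priority.

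**What to change.** In 8.11, and in the charter if it has no such rule, state that review #1 is held at the 10-subject count or by a fixed date, whichever is first. Set the date so that the meeting itself, not just the data cut, falls before the first OLE dose: about 7 weeks after the first subject's first dose. If the date comes first, the DMC says whether it also wants the 10-subject review.

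The cost is a sentence or two and at most one extra meeting of the existing committee. The drawback is that, with a 2- to 4-week data lag, the committee would see only about 2 to 4 subjects past Week 2 at 52-week enrolment and 1 to 2 at 104-week enrolment, about half of them active. That is a review of individual cases, not a comparison of arms. A maximum interval between all later reviews is not proposed: under slow enrolment it would add several meetings to a schedule of four, and it is not needed to secure the early look.

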8.12. Interim Analyses

To determine if Part 2 of the study should be initiated, an interim analysis will be conducted when all the randomized subjects from Part 1 have completed the Week 8 visit or discontinued from the study. Unblinded data from Part 1 will be used to evaluate drug safety and efficacy, which may result in a study amendment before the initiation of Part 2 of the study.

A Gilead internal unblinded team independent of the blinded study team will be assembled at the beginning of the study, which consists of medical monitor, statistical programmer, biostatistician and other personnel if necessary. The Gilead internal unblinded team will be granted the access to unblinded clinical data including treatment assignment to closely monitor study progress and drug safety. To mitigate the risks of inadvertently releasing the treatment information to the sites and subjects, the internal team will keep the unblinded information confidential and will not communicate the information to blinded study team, site staff or subjects. Data unblinding due to medical emergency will follow standard Gilead procedures.

9. RESPONSIBILITIES

9.1. Investigator Responsibilities

9.1.1. Good Clinical Practice

The investigator will ensure that this study is conducted in accordance with the principles of the Declaration of Helsinki (as amended in Edinburgh, Tokyo, Venice, Hong Kong, and South Africa), International Conference on Harmonisation (ICH) guidelines, or with the laws and regulations of the country in which the research is conducted, whichever affords the greater protection to the study subject. These standards are consistent with the European Union Clinical Trials Directive 2001/20/EC and Good Clinical Practice Directive 2005/28/EC.

The investigator will ensure adherence to the basic principles of Good Clinical Practice, as outlined in 21 CFR 312, subpart D, "Responsibilities of Sponsors and Investigators," 21 CFR, part 50, 1998, and 21 CFR, part 56, 1998.

The investigator and all applicable subinvestigators will comply with 21 CFR, Part 54, 1998, providing documentation of their financial interest or arrangements with Gilead, or proprietary interests in the investigational drug under study. This documentation must be provided prior to the investigator's (and any subinvestigator's) participation in the study. The investigator and subinvestigator agree to notify Gilead of any change in reportable interests during the study and for 1 year following completion of the study. Study completion is defined as the date when the last subject completes the protocol-defined activities.

9.1.2. Institutional Review Board (IRB)/Independent Ethics Committee (IEC) Review and Approval

The investigator (or sponsor as appropriate according to local regulations) will submit this protocol, informed consent form, and any accompanying material to be provided to the subject (such as advertisements, subject information sheets, or descriptions of the study used to obtain informed consent) to an IRB/IEC. The investigator will not begin any study subject activities until approval from the IRB/IEC has been documented and provided as a letter to the investigator.

Before implementation, the investigator will submit to and receive documented approval from the IRB/IEC any modifications made to the protocol or any accompanying material to be provided to the subject after initial IRB/IEC approval, with the exception of those necessary to reduce immediate risk to study subjects.

9.1.3. Informed Consent

The investigator is responsible for obtaining written informed consent from each individual participating in this study after adequate explanation of the aims, methods, objectives, and potential hazards of the study and before undertaking any study-related procedures.

The investigator must use the most current IRB or IEC-approved consent form for documenting written informed consent. Each informed consent (or assent as applicable) will be appropriately signed and dated by the subject or the subject's legally authorized representative and the person conducting the consent discussion, and also by an impartial witness if required by IRB or IEC or local requirements. The consent form will inform subjects about genomic testing and sample retention, and their right to receive clinically relevant genomic analysis results.

9.1.4. Confidentiality

The investigator must assure that subjects' anonymity will be strictly maintained and that their identities are protected from unauthorized parties. Only subject initials, date of birth, another unique identifier (as allowed by local law) and an identification code will be recorded on any form or biological sample submitted to the Sponsor, IRB/IEC, or laboratory. Laboratory specimens must be labeled in such a way as to protect subject identity while allowing the results to be recorded to the proper subject. Refer to specific laboratory instructions.

NOTE: The investigator must keep a screening log showing codes, names, and addresses for all subjects screened and for all subjects enrolled in the trial. Subject data will be processed in accordance with all applicable regulations.

The investigator agrees that all information received from Gilead, including but not limited to the investigator brochure, this protocol, CRF/eCRF, the IMP, and any other study information, remain the sole and exclusive property of Gilead during the conduct of the study and thereafter. This information is not to be disclosed to any third party (except employees or agents directly involved in the conduct of the study or as required by law) without prior written consent from Gilead. The investigator further agrees to take all reasonable precautions to prevent the disclosure by any employee or agent of the study site to any third party or otherwise into the public domain.

9.1.5. Study Files and Retention of Records

The investigator must maintain adequate and accurate records to enable the conduct of the study to be fully documented and the study data to be subsequently verified. These documents should be classified into at least the following two categories: (1) investigator's study file, and (2) subject clinical source documents.

The investigator's study file will contain the protocol/amendments, CRF and query forms, IRB/IEC, and governmental approval with correspondence, informed consent, drug records, staff curriculum vitae and authorization forms, and other appropriate documents and correspondence.

The required source data should include sequential notes containing at least the following information for each subject:

- Subject identification (name, date of birth, gender);
- Documentation that subject meets eligibility criteria, ie, history, physical examination, and confirmation of diagnosis (to support inclusion and exclusion criteria);

- Documentation of the reason(s) a consented subject is not enrolled
- Participation in study (including study number);
- Study discussed and date of informed consent;
- Dates of all visits;
- Documentation that protocol specific procedures were performed;
- Results of efficacy parameters, as required by the protocol;
- Start and end date (including dose regimen) of study drug, including dates of dispensing and return;
- Record of all adverse events and other safety parameters (start and end date, and including causality and severity);
- Concomitant medication (including start and end date, dose if relevant; dose changes);
- Date of study completion and reason for early discontinuation, if it occurs.

All clinical study documents must be retained by the investigator until at least 2 years or according to local laws, whichever is longer, after the last approval of a marketing application in an ICH region (ie, United States, Europe, or Japan) and until there are no pending or planned marketing applications in an ICH region; or, if no application is filed or if the application is not approved for such indication, until 2 years after the investigation is discontinued and regulatory authorities have been notified. Investigators may be required to retain documents longer if specified by regulatory requirements, by local regulations, or by an agreement with Gilead. The investigator must notify Gilead before destroying any clinical study records.

Should the investigator wish to assign the study records to another party or move them to another location, Gilead must be notified in advance.

If the investigator cannot provide for this archiving requirement at the study site for any or all of the documents, special arrangements must be made between the investigator and Gilead to store these records securely away from the site so that they can be returned sealed to the investigator in case of an inspection. When source documents are required for the continued care of the subject, appropriate copies should be made for storage away from the site.

9.1.6. Case Report Forms

For each subject consented, an eCRF will be completed by an authorized study staff member whose training for this function is documented according to study procedures. eCRF should be completed on the day of the subject visit to enable the sponsor to perform central monitoring of safety data. Subsequent to data entry, a study monitor will perform source data verification

within the EDC system. Original entries as well as any changes to data fields will be stored in the audit trail of the system. Prior to database lock (or any interim time points as described in the clinical data management plan), the investigator will use his/her log in credentials to confirm that the forms have been reviewed, and that the entries accurately reflect the information in the source documents. The eCRF capture the data required per the protocol schedule of events and procedures. System-generated or manual queries will be issued to the investigative site staff as data discrepancies are identified by the monitor or internal Gilead staff, who routinely review the data for completeness, correctness, and consistency. The site coordinator is responsible for responding to the queries in a timely manner, within the system, either by confirming the data as correct or updating the original entry, and providing the reason for the update (e.g. data entry error). At the conclusion of the trial, Gilead will provide the site with a read-only archive copy of the data entered by that site. This archive must be stored in accordance with the records retention requirements outlined in Section 9.1.5.

